**SPECIFIC AIMS**

Concisely state the objectives of the study and the hypothesis being tested.

This protocol is a randomized, double-blind, placebo-controlled clinical trial which aims to investigate the effect of a sequential anabolic and anti-resorptive strategy on BMD in women with AN receiving estrogen. We hypothesize that a sequential anabolic and anti-resorptive strategy in AN will maximally increase BMD by first stimulating low bone formation with rhIGF-1 administration and then decreasing bone resorption with risedronate.

Specific Aim 1: Sequential therapy with physiologic rhIGF-1 followed by a bisphosphonate will increase bone mineral density in women with AN more than a bisphosphonate alone or placebo.

Specific Aim 2: Sequential therapy with physiologic rhIGF-1 followed by a bisphosphonate will improve bone microarchitecture and bone strength in women with AN compared with bisphosphonate or placebo.

**BACKGROUND AND SIGNIFICANCE**

Provide a brief paragraph summarizing prior experience important for understanding the proposed study and procedures.

Anorexia nervosa (AN) is a prevalent serious disease of young women leading to severe bone loss at multiple skeletal sites. An increasingly common disorder among young women, AN is characterized by self-imposed restrictive nutritional practices and weight loss, occurring in 0.5-1.0% of college-age women in the US. The illness can persist despite psychiatric and nutritional counseling. Bone loss is a severe, frequent and often permanent comorbid medical complication of AN resulting in debilitating vertebral crush fractures. There are a number of compelling reasons why bone loss in women with AN is an important health concern. First, the prevalence, extreme rapidity and severity of bone loss results in major morbidity. Second, osteopenia is often permanent, despite recovery. Third, there are no therapies that normalize BMD or that are FDA-approved for bone loss in AN. Fourth, in contrast to postmenopausal osteoporosis in which

therapy may be life-long, the goal in patients with AN is treatment during the acute illness to reduce further bone loss and fracture risk. We propose that an early relatively short-term intervention during the period of low weight and rapid bone loss may prevent significant osteopenia and permanent increased fracture risk in women with AN.

Bone loss is prevalent and severe in young women with AN. The majority of women with AN have bone loss, and 50% have BMD measurements greater than 2 standard deviations (SD) below normative means. Bone mass in these young women may be comparable to postmenopausal women in their 7th and 8th decades. However, fracture risk is not fully explained by BMD, perhaps due to differences in bone microarchitecture between AN and healthy controls that is not captured by BMD. Of major importance is the fact that although BMD increases with weight recovery, osteopenia is often a permanent consequence of AN. Significant persistent osteopenia in women with AN has been shown in many studies and both cortical and trabecular BMD remain low more than ten years after recovery. Because bone mass remains persistently low despite recovery, such women remain at a high fracture risk throughout life, estimated to be 7.1 times that of healthy women in this age range. These data suggest that there may be a therapeutic window during which effective treatment should be implemented to prevent significant, lifelong bone mass reduction in this vulnerable population.

Low bone formation and high bone resorption underlie bone loss in AN. AN in adult women is characterized by a negative balance in bone metabolism, with decreased bone formation and increased bone resorption. Unlike many other states of estrogen deficiency, bone formation is profoundly suppressed and bone resorption increased. This dissociation of bone formation and resorption is a key mechanism underlying the severe degree of osteopenia in this disease. Therefore, an ideal therapy for bone loss in AN must address both low bone formation as well as decreased bone resorption. data demonstrate significant increases in BMD, but not to normal, with risedronate and with IGF-1, when administered separately, but neither alone addresses the severe degree of BMD observed in women with AN.

IGF-1 deficiency is a key etiologic factor underlying low bone formation and low bone mass in AN. Correcting IGF-1 deficiency effectively increases bone formation and BMD in AN. Based on , the scientific rationale for IGF-1 physiologic replacement in AN, and the demonstrated safety of IGF-1, rhIGF-1 is an ideal strategy for use as an anabolic agent in young women with AN. data also provide strong evidence supporting the effectiveness of risedronate to decrease bone resorption and increase BMD in young women with AN. We hypothesize that bisphosphonates, because of their potent anti-resorptive effects, will consolidate the anabolic effects of rhIGF-1 to increase BMD in AN. We propose that maximal effectiveness to increase bone mass in AN will be achieved with sequential therapy with 6 months of rhIGF-1 followed by 6 months of risedronate. We propose that this therapy may be effective in reversing bone loss and increasing BMD during a time of active disease.

## **RESEARCH DESIGN AND METHODS**

Briefly describe study design and anticipated enrollment, i.e., number of subjects to be enrolled by researchers study-wide and by Partners researchers. Provide a brief summary of the eligibility criteria (for example, age range, gender, medical condition). Include any local site restrictions, for example, "Enrollment at Partners will be limited to adults although the sponsor's protocol is open to both children and adults."

**Subjects:** Over the proposed 5 years, 200 women with AN will be recruited for an evaluable population of 90 women, 18-45 years old (assuming a 10% drop-out rate based on our previous studies). Subjects with AN will be randomized 2:2:1 in a double-blind fashion for 12 months: 1) sequential therapy with rhIGF-1 [REDACTED] for 6 months followed by 6 months of risedronate [REDACTED], 2) risedronate [REDACTED] or 3) double-placebo to determine effects on BMD, bone microarchitecture, and bone strength at trabecular and cortical sites. All subjects will meet the DSM-V criteria for AN and will be assessed for study suitability and monitored throughout the grant period for their overall psychiatric clinical state in coordination with the patients' clinical care team by a study psychiatrist, psychologist or psychiatric nurse practitioner. A standard oral contraceptive pill [REDACTED] or a standard transdermal estrogen patch [REDACTED] will be offered to potential subjects who are otherwise eligible to participate in the study but who are not currently receiving estrogen orally, transvaginally, or transdermally, nor have had their menses in the past two to three months. This medication will be prescribed at the lowest effective dose and for the shortest duration of time possible. Oral contraceptives or an estrogen patch will not be offered to any potential study participant with absolute or relative contraindications to estrogen use. We will not prescribe unopposed estrogen to any participant with an intact uterus. For such women who are not already receiving a progestin, we will concurrently provide [REDACTED] [REDACTED] [REDACTED]

### **Inclusion/Exclusion Criteria:**

#### **Inclusion Criteria, AN:**

- Age 18-45 years
- AN defined by DSM-V diagnostic criteria
- Oral contraceptive use or transdermal or transvaginal administration of estrogen prior to the baseline visit, or willingness to start oral contraceptives or estrogen at baseline visit, or evidence that the patient is estrogen replete, i.e. menses within the previous two to three months
- BMD T score or Z score < -1.0 measured within 6 months of the screening visit.
- Normal TSH or free T4
- Normal serum 25-OH vitamin D ( $\geq 20$  ng/mL) and calcium levels
- Ongoing care from a treatment team
- Agree to use barrier contraception
- Dental check up within the past year

#### **Exclusion Criteria, AN:**

- Any subject with contraindications to risedronate
- Any subject with binge-purge subtype of anorexia nervosa who vomits regularly as their form of purging (vs. those who use laxatives or diuretics) and who have significant periodontal disease, tooth erosion or an invasive dental or periodontal procedure within the previous three months.
- Any disease known to affect bone, including untreated thyroid dysfunction, Cushing's or renal failure
- Any medication known to affect bone metabolism within 3 months of the study, excluding oral contraceptives or other forms of estrogen administration. Bisphosphonates must have been discontinued for at least one year before participation
- Serum potassium <3.0 meq/L

- Serum ALT >3 times upper limit of normal
- eGFR of less than 30 ml/min
- Pregnant and/or breastfeeding
- Diabetes mellitus
- Active substance abuse, including alcohol
- Suicidality
- History of malignancy
- Angioedema to transdermal patch
- Hypersensitivity to estradiol
- Allergy to peanuts in subjects who will take progesterone tablets
- Breast cancer
- Known, suspected, or history, hypersensitivity to progesterone,
- Thromboembolic disorders
- Significant dental procedures are probable during the study year

An additional population of 50 women with AN who have BMD T score or Z score > -1.0 will be recruited for the bone microarchitecture substudy, for an evaluable population of 30 subjects. Exclusion criteria for the substudy will otherwise be the same as for the main study.

Briefly describe study procedures. Include any local site restrictions, for example, “Subjects enrolled at Partners will not participate in the pharmacokinetic portion of the study.” Describe study endpoints.

### **Women with AN**

**Screening Visit:** A “Screening Visit” will be conducted by a member of the medical team to determine eligibility for the protocol. All subjects will be seen [REDACTED] for an outpatient visit including the following: A complete medical history, physical examination and urine pregnancy test. History taking will include complete eating disorder, weight, menstrual, and medication histories. In addition, the following will be performed:

1. Blood draw for comprehensive metabolic panel, cbc, TSH or free T4, 25-OH vitamin D2, phosphorus, and calcium level
2. Nutritional evaluation, including weight in a gown, height, frame size, calculation of percent IBW and body mass index (BMI), performed by research dieticians
3. An optional food diary will be given to subjects to fill out. This is optional for AN subjects, who could potentially experience psychological stress if required to complete food diaries.
4. DEXA scan of the spine, hip, radius, and total body if the subject has not had a DEXA scan within 6 months prior to the screening visit
5. Determination of AN diagnosis and subtype (restricting or binge/purge) using DSM-V criteria
6. Verification of the AN diagnosis
7. Verification of lack of comorbid concerns (i.e. suicidality, substance use) will occur by the study psychiatrist, psychologist, or psychiatric nurse practitioner. Suicidality is assessed through a verbal conversation with a psychiatric health professional. If the subject has been suicidal in the past, the psychiatric professional will ask questions to assess their level of

suicidality, and whether it would be a risk to their health to partake in a study. If a subject appears to be actively suicidal, study staff will reach out to their treatment team to alert them of this information and ensure that a treatment plan is in place. This plan includes if this information is discovered by screen via telephone.

**Baseline Visit:** Eligible study subjects (n=100 women with AN) will be assessed [REDACTED] for baseline testing.

1. A complete medical history including menstrual history and instructions on keeping a menstrual diary, consumptive habits (smoking, alcohol, caffeinated beverages) will be recorded, oral temperature, height and weight in gown, pulse and blood pressure, and physical examination will be performed
2. Urine pregnancy test
3. DEXA scan of the spine, hip, radius, and total body if screen visit did not take place within 1 month of BL visit or if a DEXA scan was not performed at the screening visit.
4. Baseline hormone and safety blood testing: IGF-1, glucose, ALT, potassium, PYY
5. HR-pQCT and FEA of the radius and tibia and single slice CT mid-thigh for muscle mass and cross-sectional abdominal CT at L4 for both visceral and subcutaneous abdominal fat mass respectively
6. MDCT of L1 to determine structural characteristics of the spine.
7. Functional tests of strength using the handgrip dynamometer
8. Subjects will be asked to take [REDACTED] calcium and [REDACTED] Vitamin D supplements daily throughout the study.
9. Eating Disorder Examination—Questionnaire
10. Eating Disorder Inventory-2
11. Paffenbarger Exercise Questionnaire

[REDACTED]

Eligible consented subjects will be allowed to have CT scans performed either 2 weeks before or 1 week after their baseline visit if scheduling conflicts arise with the baseline visit. This will allow the subject to obtain a baseline assessment of bone microarchitecture prior to the initiation of rhIGF-1 supplementation.

Randomization to treatment or placebo group will occur at the baseline visit. After the baseline visit, follow-up will occur at 1, 3, 4.5, 6, 7.5, 9, 10.5 and 12 months after baseline testing for follow-up testing. IGF-1 levels and glucose will be measured at each visit during the first 6 months of the study and rhIGF-1 dose titrated based on IGF-1 levels; IGF-1 will also be measured at 12 months. Pregnancy tests and clinical evaluation will be performed at each visit. A nutritional evaluation will be performed at every visit. BMD at the spine, hip, radius and total body will be performed at 6 and 12 months after baseline. HR-pQCT and FEA of the radius and tibia and cross-sectional CT to measure left thigh muscle mass and to determine abdominal fat mass (both visceral and subcutaneous) will be performed at 6 and 12 months. CT of L1 to determine structural characteristics of the spine will be performed at 12 months. Markers of bone

metabolism will be performed at months 1, 3, 6, 9 and 12. Functional tests of strength will be performed at months 6 and 12. The primary endpoint will be PA spine BMD.

Subjects who do not live locally will be able to have their blood drawn offsite for levels of IGF-1 and bone markers. Subjects who choose this option will also have a history and physical performed by a local physician for each offsite visit. For visits which involve questionnaires, those will be mailed to the subject to be completed and returned to study staff. Tests that need to be run in real time will be done at local laboratories, with the results mailed to investigators. Otherwise, the samples will be mailed to investigators. In the event that a CT cannot be performed on the scheduled visit date due to unforeseen issues, willing subjects will be able to return within a 1 month window for this test.

For studies involving treatment or diagnosis, provide information about standard of care at Partners (e.g., BWH, MGH) and indicate how the study procedures differ from standard care. Provide information on available alternative treatments, procedures, or methods of diagnosis.

No treatment thus far has been successful in increasing bone density in women with anorexia nervosa. Weight gain is associated with some increase in bone density, but is difficult to attain (occurs in only 50%) and sustain. The DXA scan is the best validated method currently used clinically to assess bone mass and fracture risk. This is the standard method of diagnosis at Partners, and is provided for free to study subjects. There are currently no FDA-approved therapies for anorexia nervosa-induced bone loss.

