A number of procedures will be instituted to protect against potential risk involved in this protocol. All patients will have pregnancy tests on admission prior to receiving any radiation or study medication. Subjects will also have serial pregnancy tests at every study visit. All study-related serious adverse events will be reported to the Subcommittee on Human Studies within 24 hours of occurrence.

Describe explicitly the methods for ensuring the safety of subjects. Provide objective criteria for removing a subject from the study, for example, objective criteria for worsening disease/lack of improvement and/or unacceptable adverse events. The inclusion of objective drop criteria is especially important in studies designed with placebo control groups.

Subjects will be instructed to call us if they develop any side-effects of the IGF-1 or risdrionate medication, or if symptoms of hypoglycemia are experienced. They will be advised to take 4 oz orange juice or two glucose pills if they are experiencing symptoms of hypoglycemia. Subsequent management will be decided based on the severity of the side-effect.

Serious side effects related to study drug will necessitate protocol discontinuation. If a subject develops a minor side effect, she will be asked to continue medications as per the protocol. Worsening of symptoms may necessitate temporarily withholding medication until other potential causes of symptoms are ruled out. Withholding medication for longer than one week will necessitate discontinuation of the study.

To minimize the risk from radiation, scans will not be performed on subjects until a negative pregnancy test result is obtained. If lab abnormalities are discovered, the subject and their physician, if authorized by the subject, will be notified.

If subjects are uncomfortable with any portion of any study visit, this portion will be discontinued or not performed.

Drop criteria for subjects:

1. Pregnancy (for any subject)
2. Medical instability, which will be determined by the study physician. Patients in this category will be assessed by the DSMB, and continue to be assessed according to study protocol
3. Serious study-related adverse event

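### Off-site tests run at local laboratories are reported to investigators by mail, with no faster written route for an abnormal safety result

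*Protocol*

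**What the plan says.** The off-site arrangement is in the Protocol, near the end of *Women with AN*. Its scope is blood drawing: "Subjects who do not live locally will be able to have their blood drawn offsite for levels of IGF-1 and bone markers". A clinician is involved each time: "Subjects who choose this option will also have a history and physical performed by a local physician for each offsite visit". On results, it says: "Tests that need to be run in real time will be done at local laboratories, with the results mailed to investigators". All other samples are mailed to the investigators.

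The schedule in the same section sets what is due at each visit. For timing, "follow-up will occur at 1, 3, 4.5, 6, 7.5, 9, 10.5 and 12 months after baseline testing". For glucose, "IGF-1 levels and glucose will be measured at each visit during the first 6 months of the study". Bone markers follow their own calendar: "metabolism will be performed at months 1, 3, 6, 9 and 12". For pregnancy testing, "Pregnancy tests and clinical evaluation will be performed at each visit". The safety text under *Alternate strategies to address low bone density in AN* repeats the last requirement: "Subjects will also have serial pregnancy tests at every study visit". Neither statement exempts off-site visits. The drop criteria in that same safety text list pregnancy first.

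The SAP is silent on off-site visits and on reporting of results.

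**The concern.** The plan singles out a class of tests that cannot wait for shipment and then reports their results by the slowest ordinary route. A local laboratory can have an abnormal value in hand on the day of the draw while the study team, which decides on study drug, waits for the post.

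Two safety items could be caught by this. Glucose is monitored in the first 6 months, when part of the sample takes rhIGF-1 under blind and the Protocol lists hypoglycemia among its risks. Pregnancy is a drop criterion, and the study team can apply it only once it knows the result. *Foreseeable Risks and Discomforts* notes that bisphosphonates stay in bone for years and that their release in pregnancy or breastfeeding is unknown. Under 2:2:1 randomization, (2 + 2)/5 = 80% of subjects are assigned an active drug in either half of the year. A local physician would not know which subjects these are.

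**Working it through.** There is no planned figure to reproduce. The check is to see which visits the mail route can reach, and then whether any other provision carries a result to the team sooner.

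**Step 1: visits and tests.** Inputs are from the follow-up schedule in *Women with AN*.

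| Month | IGF-1 | Bone markers | Glucose | Pregnancy test | Imaging |
|---|---|---|---|---|---|
| 1 | yes | yes | yes | yes | no |
| 3 | yes | yes | yes | yes | no |
| 4.5 | yes | no | yes | yes | no |
| 6 | yes | yes | yes | yes | yes |
| 7.5 | no | no | no | yes | no |
| 9 | no | yes | no | yes | no |
| 10.5 | no | no | no | yes | no |
| 12 | yes | yes | no | yes | yes |

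The off-site option is worded for IGF-1 and bone-marker draws. I assume that months 6 and 12 are attended at the study site, because BMD and CT imaging fall there. That leaves months 1, 3, 4.5 and 9, which is 4 visits. Glucose is due at 3 of them (1, 3 and 4.5) and a pregnancy test at all 4. Months 7.5 and 10.5 carry neither named draw and are not counted.

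**Step 2: which tests the mail sentence covers.** The paragraph names none. Tests needing real-time handling most naturally means those whose samples cannot be shipped. Glucose fits that description, but this is an inference. The pregnancy test is less certain: at screening, at baseline and before x-rays it is a urine test, which the local physician could do on the spot. It falls under the mail sentence only if a laboratory performs it.

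**Step 3: other possible routes.**

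- *Notice of laboratory abnormalities* (safety text): goes to the subject and, with her permission, her physician. It gives no time limit and does not name the investigators as recipients. If study staff issue it, it can start only after the mailed result arrives.
- *Call-in instruction* (safety text): covers side effects and symptoms of hypoglycemia, not a laboratory value or a positive pregnancy test.
- *24-hour rule* (safety text): covers study-related serious adverse events reported to the ethics subcommittee.
- *Scan rule* (safety text and *Foreseeable Risks and Discomforts*): holds back imaging until a negative pregnancy test. It does not affect study drug.
- *Next visit*: the gap is 1 month from baseline to month 1, 2 months from month 1 to month 3, and 1.5 months thereafter, so it is not a prompt backstop.

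None of these supplies a faster written route from a local laboratory to the study team.

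**Step 4: the word for mailing.** It could be read as electronic mail. The same paragraph also uses it for questionnaires and for physical samples, so post is the more natural reading.

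**The case against.** The strongest reply is that this is operational detail. The Protocol is an institutional form that asks for a brief description of procedures. How a local office passes on a result usually belongs in an instruction sheet. Saying that results are mailed does not forbid a telephone call, and the team already plans to phone subjects after an rhIGF-1 dose increase. This has force, and it is why the point is minor. It does not remove the point, because the plan is not silent: it names a method, and the method is slow.

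A second reply is that the residual risk is small. Subjects agree to barrier contraception, and some will also take oral contraceptives. A local physician sees the subject at each off-site visit, she is to be told of laboratory abnormalities, and she can stop the drug herself. For glucose, no stopping threshold is stated, rhIGF-1 is titrated on IGF-1, and hypoglycemia was uncommon in adult women with AN. Meal timing, carried carbohydrate and the call-in instruction apply wherever the subject is. All of this stands.

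A reader might infer something stronger: that the Protocol sends positive off-site pregnancy tests by mail, so that exposed pregnancies would go unrecognized by the team. The documents do not support that. The off-site paragraph never mentions the pregnancy test, and the mail sentence would not govern a urine test done by the local physician. In that case the Protocol simply does not say how the result is passed on, which is a matter of missing detail. A reader might also turn an assumed postal delay into a percentage of the interval between visits. That would not measure risk, and the delay itself is not stated.

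**Conclusion.** The point holds as a minor safety improvement. Off-site tests run at local laboratories are reported to investigators by mail, and nothing in the Protocol or SAP gives a faster route. The study team may therefore learn of an abnormal safety result only after a delay of unstated length.

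The exposure is at most 3 glucose results and 4 pregnancy tests per off-site subject. That rests on three assumptions: glucose is among the tests run locally, the pregnancy test is done by a laboratory, and months 6 and 12 are attended at the study site. The number of off-site subjects is not given, so no count of affected subjects can be made. The finding concerns the written plan; staff may telephone in practice. No endpoint, analysis or sample size is affected.

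**What to change.** In the off-site paragraph of *Women with AN*, replace mailing of local-laboratory safety results with same-day phone, fax or secure electronic reporting to the study physician. State which tests this covers, with glucose in the first 6 months as the obvious candidate. State who performs the off-site pregnancy test, and have that person or laboratory phone a positive result to the study physician the same day. If a call is also wanted for abnormal glucose, give the range that triggers it, since the Protocol now states no threshold.

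The cost is two or three sentences and a short instruction sheet for local laboratories and physicians. No test or visit is added, because the schedule already requires both tests.
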